¹The Medicines for Human Use (Clinical Trials) Regulations (S.I. 2004/1031) and any subsequent amendments to it.

LIST OF ABBREVIATIONS

Abbreviation	Definition
AE	Adverse Event
AJCC	American Joint Committee on Cancer
ALC	Absolute Lymphocyte Counts
ALP	Alkaline Phosphatase
ALT	Alanine Aminotransferase
ANC	Absolute Neutrophil Count
APCs	Antigen Presenting Cells
APTT	Activated Partial Thromboplastin Time
AST	Aspartate Aminotransferase
CI	Chief Investigator
CNS	Central Nervous System
CR	Complete Response
CRP	C-Reactive Protein
CT	Computed Tomography
CTA	Clinical Trial Authorisation
CTCAE	Common Terminology Criteria for Adverse Events
CTLA-4	Cytotoxic T-lymphocyte-associated protein 4
CTV	Clinical Target Volume
DAMPs	Damage Associated Molecular Patterns
DNA	Deoxyribonucleic acid
DVH	Dose Volume Histograms
ECI	Event of Clinical Interest
ECOG	Eastern Cooperative Oncology Group
eCRF	Electronic Case Report Forms
EudraCT	European Clinical Trials Database
FAS	Full analysis set
FFPE	Formalin Fixed Paraffin Embedded
GCP	Good Clinical Practice
GP	General Practitioner
GTV	Gross Tumour Volume
Gy	Gray
Hb	Haemoglobin
HIV	Human Immunodeficiency Virus
HMGB1	High Mobility Group Box 1
IB	Investigator Brochure
ICF	Informed Consent Form
ICH-GCP	International Conference on Harmonisation for Good Clinical Practice
ICMJE	International Committee of Medical Journal Editors
ICR	Institute of Cancer Research
ID	Identification
IEC	Independent Ethics Committee
IHC	immunohistochemistry
IMP	investigational medicinal product
IMRT	Intensity Modulated Radiation Therapy
IRB	Institutional Review Board

LIST OF ABBREVIATIONS

Abbreviation	Definition
irAE	Immune Related Adverse Event
irECI	Immune Related Event of Clinical Interest
ISF	Investigator Site File
ITIM	Immunoreceptor tyrosine-based inhibition motif
ITSM	Immunoreceptor tyrosine-based switch motif
ITT	Intention to Treat
IV	Intravenous
LDH	Lactate Dehydrogenase
LENT-SOMA	Late Effects of Normal Tissue – Subjective, Objective, Management.
mAb	Monoclonal Antibody
mg	milligram
MHRA	Medicines and Healthcare Regulations Agency
MRI	Magnetic Resonance Imaging
MSD	Merck, Sharp & Dohme
MTD	Maximum Tolerated Dose
NCI	National Cancer Institute
NHS	National Health Service
NSAIDS	Non-steroidal anti-inflammatory drugs
NSCLC	Non Small Cell Lung Cancer
OAR	Organ At Risk
ORR	Overall Response Rate
OS	Overall Survival
OTC	Over the Counter
PD	Progressive Disease
PD-1	Programmed Cell Death Protein 1
PD-L1	Programmed Death-Ligand 1
PFS	Progression Free Survival
PI	Principal Investigator
PIS	Patient Information Sheet
PK	Pharmacokinetic
PR	Partial Response
PT	Prothrombin Time
PTV	Planning Target Volume
Q2W	Every 2 Weeks
Q3W	Every 3 Weeks
QA	Quality Assurance
QC	Quality Control
R&D	Research and Development
RDSU	Research and Development Statistical Unit
REC	Research Ethics Committee
RECIST	Response Evaluation Criteria in Solid Tumours
RM-CTU	Royal Marsden Clinical Trials Unit
RNA	Ribonucleic acid
RR	Response Rate
RT	Radiotherapy

LIST OF ABBREVIATIONS	
Abbreviation	Definition
RTTQA	NCRI Radiotherapy Trials QA Group
SAE	Serious Adverse Event
SAR	Serious Adverse Reaction
SBRT	Stereotactic Body Radiation Therapy
SDV	Source Data Verification
SOP	Standard Operating Procedure
SPC	Summary of Product Characteristics
SUSAR	Suspected Unexpected Serious Adverse Reaction
T3	Total Triiodothyronine
T4	Free Tyroxine
TILs	Tumour-Infiltrating Lymphocytes
TMG	Trial Management Group
TSC	Trial Steering Committee
TSH	Thyroid Stimulating Hormone
ULN	Upper Limit of Normal
USM	Urgent Safety Measure
WBC	White Blood Cell
WFI	Water for Injection

1. BACKGROUND & RATIONALE

1.1. Background

1.1.1. Pharmaceutical and Therapeutic Background

The importance of intact immune surveillance in controlling outgrowth of neoplastic transformation has been known for decades [1]. Accumulating evidence shows a correlation between tumour-infiltrating lymphocytes (TILs) in cancer tissue and favourable prognosis in various malignancies [2; 3; 4; 5; 6]. In particular, the presence of CD8+ T-cells and the ratio of CD8+ effector T-cells / FoxP3+ regulatory T-cells seems to correlate with improved prognosis and long-term survival in many solid tumours. The PD-1 receptor-ligand interaction is a major pathway hijacked by tumours to suppress immune control. The normal function of PD-1, expressed on the cell surface of activated T-cells under healthy conditions, is to down-modulate unwanted or excessive immune responses, including autoimmune reactions. PD-1 (encoded by the gene *Pdcd1*) is an Ig superfamily member related to CD28 and CTLA-4 which has been shown to negatively regulate antigen receptor signalling upon engagement of its ligands (PD-L1 and/or PD-L2) [7; 8]. The structure of murine PD-1 has been resolved [9]. PD-1 and family members are type I transmembrane glycoproteins containing an Ig Variable-type (V-type) domain responsible for ligand binding and a cytoplasmic tail which is responsible for the binding of signalling molecules.

The cytoplasmic tail of PD-1 contains 2 tyrosine-based signalling motifs, an immunoreceptor tyrosine-based inhibition motif (ITIM) and an immunoreceptor tyrosine-based switch motif (ITSM). Following T-cell stimulation, PD-1 recruits the tyrosine phosphatases SHP-1 and SHP-2 to the ITSM motif within its cytoplasmic tail, leading to the dephosphorylation of effector molecules such as CD3 ζ , PKC θ and ZAP70 which are involved in the CD3 T-cell signalling cascade [7; 10; 11; 12]. The mechanism by which PD-1 down modulates T-cell responses is similar to, but distinct from that of CTLA-4 as both molecules regulate an overlapping set of signalling proteins [13; 14]. PD-1 was shown to be expressed on activated lymphocytes including peripheral CD4+ and CD8+ T-cells, B-cells, T regs and Natural Killer cells [15; 16]. Expression has also been shown during thymic development on CD4-CD8- (double negative) T-cells as well as subsets of macrophages and dendritic cells [17]. The ligands for PD-1 (PD-L1 and PD-L2) are constitutively expressed or can be induced in a variety of cell types, including non-hematopoietic tissues as well as in various tumours [18; 19; 20; 13]. Both ligands are type I transmembrane receptors containing both IgV- and IgC-like domains in the extracellular region and contain short cytoplasmic regions with no known signalling motifs. Binding of either PD-1 ligand to PD-1 inhibits T-cell activation triggered through the T-cell receptor. PD-L1 is expressed at low levels on various non-hematopoietic tissues, most notably on vascular endothelium, whereas PD-L2 protein is only detectably expressed on

antigen-presenting cells found in lymphoid tissue or chronic inflammatory environments. PD-L2 is thought to control immune T-cell activation in lymphoid organs, whereas PD-L1 serves to dampen unwarranted T-cell function in peripheral tissues [13]. Although healthy organs express little (if any) PD-L1, a variety of cancers were demonstrated to express abundant levels of this T-cell inhibitor. PD-1 has been suggested to regulate tumour-specific T-cell expansion in patients with melanoma [21]. This suggests that the PD-1/PD-L1 pathway plays a critical role in tumour immune evasion and should be considered as an attractive target for therapeutic intervention.

Pembrolizumab (previously known as MK-3475 or SCH 900475) is a potent and highly selective humanized monoclonal antibody (mAb) of the IgG4/kappa isotype designed to directly block the interaction between PD-1 and its ligands, PD-L1 and PD-L2.

1.1.2. Preclinical and Clinical Trial Data

Refer to the current Investigator's Brochure for Preclinical and Clinical data.

1.2 Rationale

1.2.1 Background

Around 13,000 patients are diagnosed with melanoma in the UK each year; the incidence of this disease is increasing more rapidly than any other type of cancer [22]. About 20% of all patients will experience metastatic relapse following primary treatment, and prognosis is poor with a median survival ranging from 9-12 months [23].

In recent years, the development of new effective drugs has revolutionized the treatment of advanced melanoma [24]. However, the response rates are still low and novel therapeutic strategies are needed. The aim of this study is to confirm whether the combination of radiotherapy and the immunotherapeutic agent pembrolizumab can increase immune responses at distant sites in advanced melanoma.

1.2.2 Pembrolizumab in melanoma

Clinical data from 135 patients with advanced melanoma treated with pembrolizumab have recently become available [25]. Confirmed response rate evaluated by central radiologic review according to the RECIST version 1.1, was 38% (95% CI, 25 to 44). The response rate did not differ significantly between patients who had received prior treatment with the anti-CTLA-4 antibody ipilimumab and those who had not (confirmed response rate, 38% [95% CI, 23 to 55] and 37% [95% CI, 26 to 49], respectively).

Responses were durable in the majority of patients (median follow-up, 11 months among patients who had a response); 81% of the patients who had a response (42 of 52) were still receiving treatment at the time of analysis in March 2013. The overall median PFS among the 135 patients was longer than 7 months. Common adverse events were fatigue, rash, pruritus, and diarrhoea. The majority of the adverse events were low grade.

Although no direct comparison has been made, efficacy results with anti-PD-1 compounds such as pembrolizumab in melanoma are superior to those achieved with the licensed anti CTLA-4 mAb ipilimumab. Thus, response rates with ipilimumab are in the order of 20% whereas with the anti-PD-1 drugs pembrolizumab or nivolumab the response rates are around 40% [26].

1.2.3 Rationale for Dose Selection

Available pharmacokinetic (PK) results in patients with melanoma, non-small cell lung cancer (NSCLC), and other solid tumour types support a lack of meaningful difference in PK exposures obtained at a given dose among tumour types. An open-label Phase 1 trial (PN001) [27] in melanoma patients has been conducted to evaluate the safety and clinical activity of single agent pembrolizumab. The dose escalation portion of this trial evaluated three dose levels, 1 mg/kg, 3 mg/kg, and 10 mg/kg, administered every 2 weeks (Q2W) in patients with advanced solid tumours. All three dose levels were well tolerated and no dose-limiting toxicities were observed. This first in human study of pembrolizumab showed evidence of target engagement and objective evidence of tumour size reduction at all dose levels (1 mg/kg, 3 mg/kg and 10 mg/kg Q2W). No maximum tolerated dose (MTD) has been identified.

In KEYNOTE-001, two randomized cohort evaluations of melanoma patients receiving pembrolizumab at a dose of 2 mg/kg versus 10 mg/kg Q3W have been completed [28]. The clinical efficacy and safety data demonstrate a lack of clinically important differences in efficacy response or safety profile at these doses. For example, in Cohort B2, advanced melanoma patients who had received prior ipilimumab therapy were randomised to receive pembrolizumab at 2 mg/kg versus 10 mg/kg Q3W. The overall response rate (ORR) was 26% (21/81) in the 2mg/kg group and 26% (25/79) in the 10 mg/kg group (full analysis set (FAS)). The proportion of patients with drug-related adverse events (AEs), grade 3-5 drug-related AEs, serious drug-related AEs, death or discontinuation due to an AE was comparable between groups or lower in the 10 mg/kg group.

Available pharmacokinetic results in patients with melanoma, NSCLC, and other solid tumour types support a lack of meaningful difference in pharmacokinetic exposures obtained at a given dose among tumour types. Population PK analysis has been performed and has confirmed the expectation that intrinsic factors do not affect exposure to pembrolizumab to a clinically meaningful extent. Taken together, these data support the use of lower doses (with similar exposure to 2 mg/kg Q3W) in all solid tumour indications. 2 mg/kg Q3W is being evaluated in NSCLC in PN001, Cohort F30 and PN010, and 200 mg Q3W is being evaluated in head and neck cancer in PN012, which are expected to provide additional data supporting the dose selection.

Selection of 200 mg as the appropriate dose for a switch to fixed dosing is based on simulation results indicating that 200 mg will provide exposures that are reasonably consistent with those obtained with 2 mg/kg dose and importantly will maintain individual patient exposures within the exposure range established in melanoma as associated with maximal clinical response. A population PK model, which characterized the influence of body weight and other patient covariates on exposure, has been developed using available data from 476 patients from PN001. The distribution of exposures from the 200 mg fixed dose are predicted to considerably overlap those obtained with the 2 mg/kg dose, with some tendency for individual values to range slightly higher with the 200 mg fixed dose. The slight increase in PK variability predicted for the fixed dose relative to weight-based dosing is not expected to be clinically important given that the range of individual exposures is well contained within the range of exposures shown in the melanoma studies of 2 and 10 mg/kg to provide similar efficacy and safety. The population PK evaluation revealed that there was no significant impact of tumour burden on exposure. In addition, exposure was similar between the NSCLC and melanoma indications. Therefore, there are no anticipated changes in exposure between different tumour types and indication settings.

1.2.4 Radiotherapy in combination with PD1 axis blockade.

In addition to its well documented cytoreductive effect preclinical evidence demonstrates that treatment with RT can lead to the generation of a CD8⁺ T lymphocyte response that has the capacity to mediate tumour cell kill [28; 29]. Treatment with radiotherapy can lead to expression of ecto-calreticulin on tumour cells as well as the release of several damage-associated molecular patterns (DAMPs) including High Mobility Group Box 1 (HMGB1) and ATP which can lead to recruitment and activation of antigen presenting cells (APCs) and priming of tumour antigen-specific T-cell responses [30; 31; 32] the potential for the generation of effective anti-cancer immune responses following radiotherapy tumour microenvironments are typically characterised as immunosuppressive, attenuating the therapeutic capacity of the immune response [33]. More recently several studies have demonstrated that the

efficacy of radiotherapy can be enhanced by combination with immunotherapy which modulates the immune response to radiation-induced tumour cell death [34; 35].

Recent preclinical data in mouse models of cancer including melanoma, demonstrate that radiotherapy leads to an increase in PD-L1 expression on the surface of cancer cells which may limit anti-tumour immune activity. These data demonstrate that blockade of the PD-1 / PD-L1 axis with either anti-PD-1 or anti-PD-L1 monoclonal antibodies leads to the generation of durable anti-tumour CD8⁺ T cell responses which significantly improve local disease control and overall survival [36]. Recently published data support this finding that local radiotherapy may generate T cell responses that are limited by PD-1 signalling [37] strongly supporting the combination strategy for the present study. Moreover, preclinical data demonstrate that only concurrent but not sequential blockade of the PD-1 / PD-L1 axis with respect to radiotherapy was effective at improving tumour control [36]; providing proof of principle for the proposed clinical trial design.

The rationale for radiotherapy dose selection is specified in Appendix 1.

2 STUDY OBJECTIVES AND ENDPOINTS

2.1 Study Objectives

2.1.1 Primary Objectives

Objective: To evaluate if radiotherapy will enhance the efficacy of pembrolizumab in the treatment of patients with metastatic melanoma by induction of an abscopal effect.

Hypothesis: Radiotherapy can potentiate the systemic immunotherapeutic activity of pembrolizumab by induction of an abscopal effect in patients with advanced melanoma.

2.1.2 Secondary Objectives

Objectives:

- To evaluate response rates by RECIST v1.1 post treatment
- To evaluate response in non-irradiated lesions
- To assess the efficacy of pembrolizumab based on Progression Free Survival (PFS).
- To assess the efficacy of pembrolizumab based on Overall Survival (OS).
- To assess the safety and tolerability of pembrolizumab alone and in combination with high dose radiotherapy.

Hypothesis: High dose radiotherapy results in immunogenic cell death resulting in release of antigens that stimulate a systemic immune response, converting the irradiated tissue into an *in situ* vaccine.

2.1.3 Exploratory Objective

Objective: Identification of biomarkers that correlate with immunological response to therapy

Hypothesis: Pembrolizumab will favourably alter the anti-tumour immune response in patients which an effect that may be increased with the combination of radiotherapy.

2.2 Study Endpoints

2.2.1 Primary Endpoint

- To evaluate improvement in tumour response rate (RR) measured by RECIST 1.1 after 12 weeks of treatment (4 cycles) of pembrolizumab or pembrolizumab and high dose radiotherapy.

2.2.2 Secondary Endpoints

- To determine response rates by RECIST v1.1 at 6 months post treatment
- To measure individual lesion response assessment every 12 weeks taking account of within patient data
- To assess the toxicity of the combination of pembrolizumab and high dose radiotherapy after 12 weeks of treatment.
- To assess PFS at 1, 2 and 3 years post treatment.
- To assess OS in the arms of the study.

2.2.3 Exploratory Endpoints

Exploratory immunological endpoints will be determined from patients consenting to both peripheral blood and tumour biopsy sampling at selected sites.

A. Peripheral blood analysis

Peripheral blood collected from patients at baseline, during and follow-up of treatment will be analysed to assess immune function in response to pembrolizumab ± radiotherapy. Assays to examine innate and/or adaptive immune functional response may include, for example, immunophenotyping, cytokine/chemokine arrays. For details, refer to the associated Trial Manual.

B. Tumour Biopsy samples

Tumour biopsy tissue collected from patients at baseline & during treatment will be examined to assess the tumour microenvironment in response to therapy. Tumour may be used in, for example, multi-

colour immunohistochemistry and RNA sequence analysis to investigate TIL infiltration & expression of known tumour-associated antigens. For details, refer to the associated Trial Manual.

3 STUDY DESIGN

3.1 Overall Study Design

This is a multicentre, open label, randomised phase II study. 234 patients with advanced melanoma will be randomised to either pembrolizumab alone or in combination with high dose radiotherapy. Randomisation will be in a 1:1 ratio and stratified to take account of their baseline LDH and previous treatment with an anti-CTLA4 agent. Patients will continue their allocated treatment regimen until they progress, discontinue study medication or withdraw. The study will be performed at a number of investigational sites in the UK.

3.2 Treatment Regimens

Patients will receive either 200mg of pembrolizumab 3 weekly alone or in combination with a high dose regimen of radiotherapy of 24Gy in 3 fractions given between the first and second doses of pembrolizumab. The patients will continue on 3 weekly doses of 200mg of pembrolizumab until disease progression, the development of unacceptable toxicities or withdrawal.

[figure not shown]
3.2.1 Additional Safety Evaluations

To ensure the safety of patients the 1st patient will be followed for 6 weeks or until the resolution of local acute toxicity to grade 1 before the second patient can begin treatment.

In addition the first 3 patients randomised to receive both pembrolizumab and radiotherapy will be seen weekly for the first 6 weeks of treatment to assess for any grade 3 or grade 4 toxicities. If no toxicity is seen the remaining patients in this arm will be seen as described above. If toxicity is seen an additional 3 patients from this arm should be seen weekly for the first 6 weeks.

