Treatment / Main Study Procedures	
Patients will be randomised to receive pembrolizumab 3 weekly either alone or in combination with a course of high dose radiotherapy. Clinical assessments will be undertaken every 3 weeks on the day on which the drug is administered. Patients will continue on this regimen until disease progression, unacceptable toxicities, discontinuation of study medication or withdrawal. Patients in the radiotherapy arm will receive 24Gy in 3 fractions over a course of 3 consecutive days between the first and second doses of pembrolizumab. Patients will also undergo tumour assessment by RECIST 1.1 every 12 weeks from the first dose of pembrolizumab (irrespective of delays in treatment) to establish disease response.
 
Please note:
 
 • The 1st patient should be followed for 6 weeks or until the resolution of local acute toxicity to grade 1 before the second patient can begin treatment. • The first 3 patients randomised to receive both pembrolizumab and

	
radiotherapy will be seen weekly for the first 6 weeks of treatment to assess for any grade 3 or grade 4 toxicity. If no toxicity is seen the remaining patients in this arm will be seen as described above. If toxicity is seen an additional 3 patients from this arm should be seen weekly for the first 6 weeks.
 
OPTIONAL: Patients in selected sites will be asked to consent to the collection of tumour biopsies and research bloods for translational endpoints. If a patient consents they will be agreeing to give both post treatment tumour biopsies and research blood samples. Tumour biopsies will be taken at their second cycle of pembrolizumab ideally from the same lesion that was used to confirm metastatic disease at screening. If this biopsy was from a lesion that had been irradiated then if possible an additional biopsy outside the radiotherapy field should also be collected. Biopsies will be core or punch biopsies. 24mls of research blood will be taken at day 1 of the first 5 cycles of pembrolizumab plus an additional sample at either time of response or progression (to be determined by treating clinician).

--	--

CHIEF INVESTIGATOR AND SPONSOR SIGNATURE PAGE

[figure not shown]
Study Title: Randomised Phase II Trial of Pembrolizumab and Radiotherapy in Melanoma (PERM)

Sponsor Protocol Number: CCR4251

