4.3. Randomisation

Patients will be randomised to receive pembrolizumab alone or in combination with radiotherapy. Randomisation will be performed on a 1:1 ratio basis and will be stratified based on the results of;

1. LDH (below or within normal range/above upper limit of the normal range) and
2. previous treatment with anti-CTLA4 agent (yes/no)

Each site will be required to complete all screening eCRFs prior to randomisation to ensure that the eligibility of the patient may be confirmed. Further information regarding randomisation procedures will be provided to sites in the study specific registration and randomisation SOP.

The patients' trial ID will be a unique that once assigned will become the permanent study identifier for that patient. In the event a patient is randomised onto the study but does not begin treatment, then that patient's trial ID will not be reassigned. **Treatment will begin within 3 days from the date of randomisation.** To ensure participant confidentiality, participants will only be identified by their assigned trial ID on eCRFs as well as on other trial specific forms and all communication to RM-CTU. It is the PI's responsibility to maintain a confidential record of the identity i.e. full name, date of birth and hospital number for the participants enrolled in this study and their assigned trial ID. At the end of the study this record should be archived along with the Site File.

PLEASE NOTE: To ensure participant safety, the first participant will be followed **for 6 weeks** or until the resolution of local acute toxicity to grade 1 **before** the second participant may commence treatment.

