Tumour Imaging	✕									✕ ³		✕ ⁴		
Targeted Physical Exam		✕			✕			✕	✕	✕	✕	✕	✕	
PEMBROLIZUMAB		✕			✕			✕	✕	✕	✕			
RADIOOTHERAPY		← Over 3 days ✕ ⁶ →												
Tumour Biopsies/Archival Tissue Collection/Correlative Studies Blood:														
Archival Tumour Collection (MANDATORY)	✕													
Diagnostic Metast’c Biopsy (MANDATORY)	✕													
Tissue Biopsy (OPTIONAL)					✕									
Research Blood Samples (OPTIONAL)		✕			✕			✕	✕	✕	✕ ⁸			

1. Cycles to be extended past cycle 5 for as long as applicable.
 
2. First 3/6 randomised to Pembrolizumab and Radiotherapy arm only.
 
3. Tumour imaging to be done every 12 weeks from the date of the 1st dose irrespective of delays in treatment cycles. Can be up to 7 days before visit to ensure results at the visit.
 
4. Only if no RECIST assessment has been completed in the last 6 weeks.
 
5. If the participant has been randomised to receive radiotherapy.
 
6. For participants randomised to radiotherapy this should be administered between the 1st and 2nd dose of pembrolizumab i.e. 24Gy in 3 fractions over 3 consecutive days
 
7. End of treatment visit assessments are only applicable if the participant comes off treatment between cycles.
 
8. A follow-up OPTIONAL Research Blood Sample can be taken at either time of response or progression (to be determined by treating clinician)
														

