6.4.2. Prohibited Concomitant Medications

Participants are prohibited from receiving the following therapies during the screening and treatment phase (including retreatment for post-complete response relapse) of this trial:

- Anti-cancer systemic chemotherapy or biological therapy
- Immunotherapy not specified in this protocol
- Radiotherapy not specified in this protocol
- Investigational agents other than pembrolizumab
- Palliative radiotherapy for symptom control
- Live vaccines within 30 days prior to the first dose of trial treatment and while participating in the trial.

Examples of live vaccines include, but are not limited to, the following: measles, mumps, rubella, chicken pox, yellow fever, rabies, BCG, and typhoid (oral) vaccine. Seasonal influenza vaccines for injection are generally killed virus vaccines and are allowed; however intranasal influenza vaccines (e.g. Flu-Mist®) are live attenuated vaccines, and are not allowed.

- Glucocorticoids for any purpose other than to modulate symptoms from an event of clinical interest of suspected immunologic etiology. The use of physiologic doses of corticosteroids may be approved after consultation with the CI/designee.

Participants who, in the assessment by the investigator, require the use of any of the aforementioned treatments for clinical management should be removed from the trial. Participants may receive other medications that the investigator deems to be medically necessary. The Exclusion Criteria describes other medications which are prohibited in this trial. There are no prohibited therapies during the Post-Treatment Follow-up Phase.

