8.3. Randomisation

Patients will be randomised in a 1:1 ratio to receive pembrolizumab alone or pembrolizumab in combination with radiotherapy using random permuted blocks within strata to take account of their LDH level at baseline and previous anti-CTLA4 treatment.

Randomisation of enrolled patients will be stratified based on the following parameters;

1. LDH (below or within normal range / above upper limit of the normal range) and
2. Previous anti-CTLA4 treatment (yes/no)

The randomisation number is a unique number. Patients will be identified using the number generated by the database which will become their unique identifier throughout the study and in all future correspondence..

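### The first-patient safety pause names no treatment arm, so under 1:1 allocation it has an even chance of being spent on a control who is never irradiated

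*Combined protocol and SAP*

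**What the plan says.** The pause appears three times:

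- **Section 3.2.1:** "the 1st patient will be followed for 6 weeks or until the resolution of local acute toxicity to grade 1 before the second patient" may start treatment.
- **Trial Summary, Treatment / Main Study Procedures:** the same rule, beginning "The 1st patient should be followed for 6 weeks".
- **Section 4.3:** "To ensure participant safety, the first participant will be followed" on the same terms.

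No arm is named in any of them. In the Summary and section 3.2.1 the next rule, weekly visits for the first three patients, is expressly limited to the combination arm.

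Allocation is 1:1, "using random permuted blocks within strata to take account of their LDH level at baseline" and previous anti-CTLA4 treatment (section 8.3). Nothing exempts the first patient or assigns that patient to radiotherapy. Section 4.3 adds: "Treatment will begin within 3 days from the date of randomisation". In the combination arm radiotherapy is "24Gy in 3 fractions given between the first and second doses of pembrolizumab" (section 3.2).

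**The concern.** The stated purpose of the pause is patient safety. Section 6.2.3 explains why caution is needed: the radiotherapy schedule is not a recognised palliative dose for melanoma, and giving it with pembrolizumab is not standard of care. A pause serves that purpose only if the patient observed has been irradiated.

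Read literally, the rule attaches to whoever enters first. If that patient is a control, the rule is satisfied and does not apply again. The first and second combination patients could then start together without breaching any stated rule. What is at stake is that single gap between irradiated patients, not the trial's inference.

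**Working it through.** The plan gives no figure for this rule, so there is none to reproduce.

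**Step 1. Chance that the first patient is a control.** In a balanced permuted block of size b, the probability that the first position is control is C(b−1, b/2−1) / C(b, b/2). For b = 2 this is 1/2, for b = 4 it is 3/6, for b = 6 it is 10/20 and for b = 8 it is 35/70. All equal 0.50. Stratification does not change this, because the first patient opens a fresh block in whichever stratum applies.

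**Step 2. Whether a control could serve as the sentinel.** Section 6.4.2 prohibits "Radiotherapy not specified in this protocol". In the schedule of assessments (section 5.1, footnote 5) the radiation toxicity review is done only "If the participant has been randomised to receive radiotherapy". Footnote 2 limits the extra weekly visits to the first 3 or 6 patients in the combination arm. A control therefore has no irradiated site, no radiation toxicity review and no extra visits.

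**Step 3. Whether another rule holds back the second irradiated patient.**

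| Safeguard | Section | Follows combination arm | Stated hold on next patient |
|---|---|---|---|
| Weekly visits for first 3, then 3 more if toxicity is seen | 3.2.1 | Yes | No |
| Trial Management Group meets every 2 weeks until first 6 complete 12 weeks | 10.8.1.1 | Yes | No |
| Toxicity review of first 6 at 12 weeks | 8.5.1 | Yes | No |
| Prospective radiotherapy plan review | 6.2.4.4 | Yes | No |

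If toxicity appears in the first three, the stated consequence is closer observation of three more, not a halt.

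**Step 4. Chance that the pause observes an irradiated patient.** Let p be the share of combination patients who do not receive radiotherapy. The plan gives no value. I assume 0 to 0.10, borrowing the overall drop-out figure in section 8.2 as an upper bound.

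| Wording | Formula | p = 0 | p = 0.10 |
|---|---|---|---|
| As written | 0.5 × (1 − p) | 0.50 | 0.45 |
| First patient randomised to the combination | 1 − p | 1.00 | 0.90 |
| First randomised to the combination who receives radiotherapy | 1 | 1.00 | 1.00 |

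**Step 5. Cost of moving the pause.** If a sentinel who is not irradiated passes the pause to the next combination patient, the expected number of pauses is 1/(1 − p), which runs from 1.00 to 1/0.9 = 1.11. Block size and stratum shares are not given, so the mean number of patients randomised before the sentinel was simulated (60,000 runs, four equal strata):

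| Assumed block size | p = 0 | p = 0.10 |
|---|---|---|
| 2 | 0.73 | 0.94 |
| 4 | 0.86 | 1.08 |
| 6 | 0.90 | 1.12 |

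Unequal strata (45/25/20/10%, assumed) give 0.71–0.90 and 0.92–1.10. At most three patients precede the sentinel in 92–99% of runs.

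The number of patients who might be irradiated without a gap cannot be derived, because no start-up accrual rate is given.

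**The case against.** The best reply is that the rule explains itself. Resolution of local acute toxicity makes sense only for an irradiated patient, so a sensible reader would apply it to the combination arm. On that view this is a drafting omission, and 50% is only the allocation ratio restated, not a measure of harm. The randomisation SOP, the treatment figure and the study flowchart were not available and may name the arm. The combination arm is also closely watched by other means. Finally, the ranges for cost and non-receipt rest on assumptions, and a remedy that halts all randomisation goes further than adding the arm's name.

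Much of this stands. The intent was probably the combination arm, the ranges are assumptions, and the arm-specific monitoring limits the consequence. Three things remain:

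- The authors named the arm in the very next rule of the Summary and section 3.2.1. Section 4.3, which governs randomisation, has no such neighbouring sentence to guide the reader. With 15–24 sites, a safety rule should not depend on inference.
- None of the other safeguards is stated to separate the first irradiated patient from the second.
- The existing rule already stops every later patient from starting, so pausing randomisation is no wider in kind. It also avoids randomising patients who could not start within 3 days. One drawback is real: radiotherapy can fall at any point between doses 1 and 2, so it may take up to about 3 weeks to learn that a sentinel will not be irradiated.

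**Conclusion.** The concern holds, as a minor point. On a literal reading there is a 50% chance that the only stated pause is used on a control. That figure needs only the 1:1 allocation and no assumption about block size. The chance that the pause observes an irradiated patient is 0.45–0.50, where the lower end assumes that 10% of combination patients are not irradiated.

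The loss is limited to the gap between the first and second irradiated patients. Confidence is medium, because the wording hints at the intended arm and the unseen SOP or figures may settle it. Even then the three protocol statements should be corrected.

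**What to change.** In the Trial Summary, section 3.2.1 and section 4.3, replace the first patient or participant with **the first patient randomised to pembrolizumab plus radiotherapy who receives radiotherapy**. Then state that:

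- the existing follow-up criterion must be met in that patient before a second combination patient starts treatment;
- randomisation is paused from the allocation of the first combination patient, which keeps the 3-day start rule workable;
- if that patient does not receive radiotherapy, randomisation reopens and the pause passes to the next combination patient;
- controls randomised before the pause start treatment as planned.

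The follow-up criterion itself is unchanged. Its two alternatives are joined by "or", so the gap may still end before 6 weeks.

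The cost is wording in three places and a pause that comes about one patient later (0.7–1.1 on the assumptions above), with 1.00–1.11 expected pauses instead of 1. Patients in screening when the pause begins may need repeat laboratory tests (7-day limit, section 4.4.1) or may outrun the 28-day screening window (section 5.1). The present rule has the same effect on the second patient.
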